1. LIST OF ABBREVIATIONS AND DEFINITIONS OF TERMS

Abbreviation or Term	Definition
AA	Arachidonic acid
AE	Adverse Event
ALT	Alanine Aminotransferase
Apo A-I	Apolipoprotein A-I
Apo A-II	Apolipoprotein A-II
Apo A-V	Apolipoprotein A-V
Apo B	Apolipoprotein B
Apo C-III	Apolipoprotein C-III
Apo E	Apolipoprotein E
AUC	Area under the curve
BP	Blood Pressure
CEC	Clinical Endpoint Committee
CHF	Congestive Heart Failure
CV	Cardiovascular
CVD	Cardiovascular Disease
DHA	Docosahexaenoic acid
DPA	Docosapentaenoic acid
ECG	Electrocardiogram
eGFR	Estimated Glomerular Filtration Rate
EPA	Eicosapentaenoic Acid
HDL2	High Density Lipoprotein subfraction HDL2
HDL3	High Density Lipoprotein subfraction HDL3
HDL-P	High Density Lipoprotein Particle Number
hsCRP	High-Sensitivity C-Reactive Protein
hsTNT	High-sensitivity troponin T
ICD	Implantable Cardioverter Defibrillator
IL-6	Interleukin 6
ITT	Intent-to-Treat
LDL-C	Low Density Lipoprotein Cholesterol
LDL-P	Low Density Lipoprotein Particle Number
LDL-TG	Low Density Lipoprotein Triglyceride
Lp(a)	Lipoprotein a
LPL	Lipoprotein Lipase
LpPLA2	Lipoprotein-associated Phospholipase-A2

Abbreviation or Term	Definition
AA	Arachidonic acid
MALE	Major Adverse Limb Event
MI	Myocardial Infarction
NAFLD	Nonalcoholic Fatty Liver Disease
NFS	NAFLD Fibrosis Score
NT-proBNP	N-terminal-pro-brain Natriuretic Peptide
Ox-LDL	Oxidized Low Density Lipoprotein
RLP-C	Remnant Lipoprotein Cholesterol
SAP	Statistical Analysis Plan
SMI	Silent Myocardial Infarction
TG	Triglycerides
ULN	Upper Limit of Normal
US	United States

2. INTRODUCTION

This purpose of this Pre-Specified List of Additional Analyses (PLAA) is to document any additional pre-specified exploratory statistical analyses that may be carried out beyond those that were pre-specified in the approved statistical analysis plan (SAP) version dated 08 July 2016 as well as the SAP Addendum dated 15 August 2018. This PLAA identifies pre-specified analyses that may or may not be performed and the results of which may or may not appear in the CSR depending upon overall results from the trial. This PLAA will be finalized and signed off prior to database lock and unblinding.

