2. INTRODUCTION

The purpose of this Statistical Analysis Plan (SAP) Addendum is to describe and document additional pre-specified statistical analyses and specifications beyond those that were pre-specified in the approved SAP version dated 08 July 2016, which will be included in the final analysis and reporting of clinical data collected during the conduct of Protocol AMR-01-01-0019. As discussed and agreed with the Food and Drug Administration (FDA) in relation to a pre-sNDA meeting on 07 March 2018, this SAP Addendum has been developed and will be finalized and submitted to the AMR101 investigational new drug application prior to database lock and unblinding. Importantly, the additional efficacy endpoints and analyses outlined below in this SAP Addendum are exploratory in nature and will not be included in the formal SAP testing scheme. Results from the exploratory analyses described herein will be included in the AMR-01-01-0019 clinical study report (CSR). Analyses associated with a separate document, entitled “pre-specified list of additional analyses (PLAA)”, that will be approved by the sponsor prior to database lock and unblinding but that may or may not be performed and the results of which may or may not appear in the CSR.

For each section below, the relevant section of the SAP will be identified.

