3. ADDITIONAL EXPLORATORY EFFICACY ANALYSES

The following list presents additional pre-specified exploratory efficacy analyses that could be of interest to the general clinical and scientific community:

- Non-fatal myocardial infarction (MI) (including both clinical manifestation and silent MI categorizations) – intent-to-treat (ITT) Population
- Evaluation of effect of time-weighted (or area under the curve [AUC]) eicosapentaenoic acid (EPA) data on the primary and key secondary composite endpoints – ITT Population
- Sensitivity analyses on the primary and key secondary composite endpoints by excluding elective coronary artery revascularizations if onset is <3 months post randomization; and also excluding peri-procedural MIs – ITT Population
- Two silent MI (SMI) sensitivity analyses on the primary and key secondary composite endpoints – ITT Population:
 - counting all potential SMIs identified by Clinical Endpoint Committee (CEC) electrocardiogram (ECG) reviewer, whether confirmed at final ECG or not; and,
 - counting only potential SMIs that have at least one confirmatory ECG showing persistence of Q-waves (even if not present at final ECG)
- Non-alcoholic fatty liver disease (NAFLD) analyses using NAFLD Fibrosis Score (NFS), assessing – ITT Population:
 - effect on primary and key secondary composite endpoints by baseline NFS category; and,
 - treatment effect on change from baseline in NFS at 1 and 5 years
- Individual and combined on-treatment goal achievement of triglyceride (TG) ≤ 150 mg/dL and hsCRP ≤ 2 mg/L at 2 years, and end of study – ITT Population
- Additional renal function (eGFR) analyses – ITT Population:
 - primary and key secondary composite endpoints for patients with baseline renal dysfunction [eGFR] ≥ 60 and < 90 mL/min/1.73m²

- treatment effect on change from baseline in renal function (eGFR) at 1 and 5 years
- Sensitivity analyses on the primary and key secondary composite endpoints by excluding patients with post-randomization low density lipoprotein cholesterol (LDL-C) values >100 mg/dL; and another for >70 mg/dL – ITT Population
- Analyses of hospitalization data (pooled positively adjudicated unstable angina requiring hospitalization, congestive heart failure [CHF] requiring hospitalization, and cardiac arrhythmia requiring hospitalization) – ITT Population
 - Time from randomization to first hospitalization
 - Recurrent event analysis on hospitalization

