- Additional subgroup analyses (United States [US] versus Non-US) on the primary and key secondary composite endpoints; also potentially other endpoints – ITT Population
- Additional subgroup analyses for patients with very high-risk cardiovascular disease (CVD) (defined as recurrent cardiovascular [CV] events or CV events in more than one vascular bed, i.e., polyvascular disease) on the primary and key secondary composite endpoints; also potentially other endpoints – ITT Population
- Sensitivity analyses for apolipoprotein B (apo B) to assess whether subgroup(s) with apo B reductions from baseline beyond certain threshold(s) have corresponding incremental reductions in clinical endpoint events
- Sensitivity analyses for endpoints comprised of myocardial infarctions which exclude peri-procedural MIs (Type 4a)
 - Additional analyses factoring for recency and number of prior MIs
- Sensitivity analyses for stroke, factoring for patients with history of stroke
- Sensitivity analyses for heart failure, factoring for patients with history of heart failure
- Sensitivity analyses for endpoints comprised of coronary revascularizations which exclude early elective revascularizations (e.g., within 30-90 days post-randomization)
- Subgroup analyses of primary and potentially key secondary endpoints among the following cohorts:
 - High risk patients with “the hypertriglyceridemic waist” (obese patients at high CV risk)
 - High risk subgroup defined by baseline high-sensitivity troponin T (hsTNT) level (and potentially by N-terminal-pro-brain Natriuretic Peptide [NT-proBNP] from archived frozen samples)
 - High TG/low LDL-C phenotypes beyond those currently specified in the SAP and SAP Addendum

- High-risk patients as defined by their atherothrombotic risk score (Bohula 2016)
- Treatment effect on:
 - Peripheral arterial events (e.g., major adverse limb [MALE] events)
 - Hypertension, using blood pressure (BP) as a continuous variable
- Using archived frozen serum biosamples, additional analyses of fatty-acid levels (and ratios) not currently specified in the SAP Addendum, including baseline and on-treatment effects on EPA, docosahexaenoic acid (DHA), docosapentaenoic acid (DPA), arachidonic acid (AA) (and associated ratios) and relationships between fatty-acid levels and cardiovascular outcomes.
 - Relationship between on-treatment fatty-acid levels and
 - baseline fatty-acid levels and
 - study medication compliance

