- Using archived frozen biosamples (serum and whole blood); potential analyses of treatment effects on biomarkers and genetic markers and associations with outcomes, including but not limited to the following:
 - Low density lipoprotein particle number (LDL-P)
 - Remnant lipoprotein cholesterol (RLP-C) (measured)
 - Low density lipoprotein triglyceride (LDL-TG)
 - Oxidized low density lipoprotein (Ox-LDL)
 - Galectin-3
 - Lipoprotein a (Lp(a)) at baseline, as a predictor of CVD benefit
 - Lipoprotein-associated phospholipase-A2 (LpPLA2)
 - High density lipoprotein subfraction 2 (HDL2), high density lipoprotein subfraction 3 (HDL3), apolipoprotein A-I (apo A-I), apolipoprotein A-II (apo A-II), high density lipoprotein particle number (HDL-P), apolipoprotein C-III (apo C-III) (and apo C-III in apo-B containing proteins), apolipoprotein A-V (apo A-V), apolipoprotein E (Apo E) subtypes (2, 3, 4), interleukin 6 (IL-6), lipoprotein lipase (LPL)
 - Analyses may include change (and percent change) from baseline, and on-treatment comparisons between treatment groups with testing as predictors of CV risk
- Exploratory analyses of differential treatment effects for potential benefit (from adverse event reports) of:
 - ophthalmologic changes (e.g., incidence of age-related macular degeneration, progression of diabetic retinopathy)

- cognitive impairment (Schwarz 2018)
- erectile dysfunction (Shim 2016)
- ischemic cardiomyopathy (as indicated by hospitalization for CHF, implantable cardioverter defibrillator [ICD] placement etc.)
- Additional genetic bioassays not included in the REDUCE-IT SAP including genes which may relate to triglyceride, lipid metabolism, and CVD
- Effects of potential mediators identified *post hoc* on primary/key secondary outcome measures (Inzucchi 2018)

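### The list of additional analyses (PLAA) lets CSR reporting of its pre-specified exploratory analyses depend on the overall trial results, with no record of what was run or left out

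*Combined protocol and SAP*

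**What the plan says.** PLAA section 2 sets the rule. Its pre-specified analyses are optional to perform, "the results of which may or may not appear in the CSR depending upon overall results from the trial". On timing it adds: "This PLAA will be finalized and signed off prior to database lock and unblinding". Section 3 introduces its list as "additional pre-specified exploratory efficacy analyses that could be of interest to the general clinical and scientific community", and section 4 introduces a safety list in the same way.

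SAP Addendum section 2 describes the PLAA as containing analyses that "may or may not be performed and the results of which may or may not appear in the CSR", without the results condition. The same section says that the Addendum's own analyses, which are also exploratory, will be included in the CSR.

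Two general statements bear on this. SAP section 2 says that analyses needed to supplement the SAP will be identified in the CSR. Protocol section 18 commits to publishing the study results whether they are positive or negative.

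**The concern.** Fixing a list before unblinding protects a reader only if the choice from the list is also fixed, or if everything run is shown. Here the choice is open after unblinding, it is tied to the results, and no count of analyses performed is promised. A reader shown a PLAA result described as pre-specified cannot tell how many companion analyses were run and left out, so a nominal p-value or a reassuring sensitivity analysis is hard to weigh.

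The stakes are highest for the listed checks on how primary events are defined. An unfavourable one could be omitted from the CSR in full compliance with the plan.

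**Working it through.** **1. Is confirmatory error touched?** The PLAA states no number of tests, alpha or error rate, so the only figures to reproduce are those of the confirmatory design. Inputs (iSAP sections 2 and 2.1): 1612 events, HR 0.85, 1:1 allocation, looks at 60%, 80% and 100%, one-sided alpha 0.025. The spending function is α(t) = 2[1 − Φ(z₀.₀₁₂₅/√t)], which gives 0.0038 at t = 0.6, 0.0122 at t = 0.8 and 0.0250 at t = 1. The boundaries are 2.669, 2.289 and 2.031, with one-sided levels 0.0038, 0.0110 and 0.0211. With drift √(1612/4) × |ln 0.85| = 3.26, power is 0.897. All agree with iSAP Table 1. SAP section 4.3.6 treats everything outside the hierarchy as exploratory, so the PLAA spends none of this alpha.

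**2. The reporting rules side by side.**

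| Source | Status of analyses | CSR reporting |
|---|---|---|
| SAP Addendum section 2 | exploratory | mandatory |
| PLAA section 2 | exploratory | optional, tied to overall results |
| SAP section 2 | any needed supplement to the SAP | to be identified in the CSR |
| Protocol section 18 | study results | published, positive or negative |

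The exploratory label cannot explain the PLAA's looser rule, because the Addendum analyses carry the same label.

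**3. Which checks are found only in the optional list?**
- *Silent MI.* SAP sections 3.2.1.1 and 4.7.1.2 vary only the event date. Whether an unconfirmed silent MI counts at all is varied only in PLAA section 3. Protocol Appendix B section 23.4 lets the last ECG decide when Q waves are evanescent.
- *Peri-procedural MI.* Appendix B section 23.4 notes that its prognosis may differ from that of spontaneous MI and that separate evaluation will be considered. The exclusion analysis appears only in PLAA section 3.
- *Early elective revascularization.* This exclusion also appears only in PLAA section 3, and in two forms: onset under 3 months in one bullet, and an example window of 30 to 90 days in another. The window could therefore be chosen after unblinding.

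**4. Which items are not fixed?** Two PLAA subgroup items are specified "on the primary and key secondary composite endpoints; also potentially other endpoints". The apo B item leaves its thresholds unstated, and the archived-sample biomarker list is expressly not exhaustive. The last efficacy bullet begins "Effects of potential mediators identified" and goes on to say that identification is post hoc.

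**5. Illustration only.** Suppose one test per top-level efficacy bullet (k = 23), every null true, and two-sided 5%. The 5% is borrowed from the tertiary-endpoint rule in SAP section 4.3.6, since the PLAA states no level. If independent, P(at least one p < 0.05) = 1 − 0.95²³ = 0.69, with 23 × 0.05 = 1.15 expected. For equicorrelated tests:

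| Correlation | Any p < 0.05 | Any in the favourable direction (0.025) |
|---|---|---|
| 0 | 0.69 | 0.44 |
| 0.5 | 0.45 | 0.23 |
| 0.8 | 0.24 | 0.12 |
| 0.95 | 0.12 | 0.06 |

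The last row matters for re-runs of the primary analysis with a few events removed. Dropping a fraction f of events leaves a correlation of about √(1 − f) with the primary result, so an assumed f of 5% to 10% gives 0.97 to 0.95.

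**The case against.** The best defence is that the condition is the trial's overall result. A natural reading is that mechanistic and archived-sample work is worth pursuing only if the trial result warrants it. The items are called exploratory in the PLAA itself, they lie outside the testing hierarchy, and the mediator item openly says post hoc. All of this stands. A reader might infer that the plan filters items by their own p-values, or that whatever is reported would be false. The documents do not support either inference: the first rule is not stated (though nothing excludes it), and the second holds only if every null is true and only nominally significant items are shown.

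A reader might also infer that the robustness of the primary result is left to the sponsor's discretion. That goes too far. The SAP commits to:
- mITT and PP analyses (4.7.1.1);
- date variants for silent MI, undetermined deaths censored, and censoring at drug discontinuation (4.7.1.2);
- each primary component separately (4.7.2);
- composites limited to non-elective revascularization, and elective revascularization on its own (4.7.4).

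The key secondary endpoint contains no revascularization, and Addendum section 4 adds on-treatment analyses. Only the three checks in step 3 remain optional.

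SAP section 2 and protocol section 18 could be said to cure the problem. They are general, while the PLAA clause is later and specific to these analyses, so they show an inconsistency without overriding it.

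Finally, genetic and archived-sample assays are run at the sponsor's discretion and may follow the CSR (protocol sections 6.3.1.3 and 6.3.1.5). A demand that every item be in the CSR would be unworkable, and the fix allows deferral.

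**Conclusion.** The point holds as a reporting and labelling defect. As written, the plan allows CSR reporting of its PLAA analyses to depend on overall results, with no denominator, and this is inconsistent with the mandatory reporting of the Addendum analyses. The results condition may attach grammatically to reporting alone; performance is optional on either reading.

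The reach is 23 top-level efficacy bullets and 3 safety bullets, including three event-definition checks on the primary composite found nowhere else. The effect on confirmatory type I error is nil. The probabilities in the working rest on an all-null assumption, an approximate test count, an unknown correlation and an inferred 5% level. They show why a denominator is needed and do not measure harm. This should be corrected, but it does not threaten the primary or secondary inference.

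**What to change.** 1. Delete the results condition from PLAA section 2, and align SAP Addendum section 2 with the new wording.
2. Commit that every PLAA efficacy or safety analysis (sections 3 and 4) performed by the time of the CSR is reported there or in an appendix, whatever its result. Add a table marking each item performed, not performed or deferred (for example archived-sample and genetic assays), with a reason not based on results.
3. Commit to the three event-definition sensitivity analyses for the primary composite: peri-procedural MI excluded, early elective revascularization excluded with one fixed window, and the silent-MI ECG-confirmation variants. Do the same for the key secondary where the exclusion can change it; the revascularization exclusion cannot.
4. Do not describe as pre-specified any item whose endpoint, cut point or mediator is not fixed in the list.

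The cost is a wording change before database lock, a longer CSR with extra appendix tables, and visibility of less favourable exploratory results. It needs no new patients, data or alpha.

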3. ADDITIONAL EXPLORATORY EFFICACY ANALYSES

The following list presents additional pre-specified exploratory efficacy analyses that could be of interest to the general clinical and scientific community:

- Non-fatal myocardial infarction (MI) (including both clinical manifestation and silent MI categorizations) – intent-to-treat (ITT) Population
- Evaluation of effect of time-weighted (or area under the curve [AUC]) eicosapentaenoic acid (EPA) data on the primary and key secondary composite endpoints – ITT Population
- Sensitivity analyses on the primary and key secondary composite endpoints by excluding elective coronary artery revascularizations if onset is <3 months post randomization; and also excluding peri-procedural MIs – ITT Population
- Two silent MI (SMI) sensitivity analyses on the primary and key secondary composite endpoints – ITT Population:
 - counting all potential SMIs identified by Clinical Endpoint Committee (CEC) electrocardiogram (ECG) reviewer, whether confirmed at final ECG or not; and,
 - counting only potential SMIs that have at least one confirmatory ECG showing persistence of Q-waves (even if not present at final ECG)
- Non-alcoholic fatty liver disease (NAFLD) analyses using NAFLD Fibrosis Score (NFS), assessing – ITT Population:
 - effect on primary and key secondary composite endpoints by baseline NFS category; and,
 - treatment effect on change from baseline in NFS at 1 and 5 years
- Individual and combined on-treatment goal achievement of triglyceride (TG) ≤ 150 mg/dL and hsCRP ≤ 2 mg/L at 2 years, and end of study – ITT Population
- Additional renal function (eGFR) analyses – ITT Population:
 - primary and key secondary composite endpoints for patients with baseline renal dysfunction [eGFR] ≥ 60 and < 90 mL/min/1.73m²

- treatment effect on change from baseline in renal function (eGFR) at 1 and 5 years
- Sensitivity analyses on the primary and key secondary composite endpoints by excluding patients with post-randomization low density lipoprotein cholesterol (LDL-C) values >100 mg/dL; and another for >70 mg/dL – ITT Population
- Analyses of hospitalization data (pooled positively adjudicated unstable angina requiring hospitalization, congestive heart failure [CHF] requiring hospitalization, and cardiac arrhythmia requiring hospitalization) – ITT Population
 - Time from randomization to first hospitalization
 - Recurrent event analysis on hospitalization
- Additional subgroup analyses (United States [US] versus Non-US) on the primary and key secondary composite endpoints; also potentially other endpoints – ITT Population
- Additional subgroup analyses for patients with very high-risk cardiovascular disease (CVD) (defined as recurrent cardiovascular [CV] events or CV events in more than one vascular bed, i.e., polyvascular disease) on the primary and key secondary composite endpoints; also potentially other endpoints – ITT Population
- Sensitivity analyses for apolipoprotein B (apo B) to assess whether subgroup(s) with apo B reductions from baseline beyond certain threshold(s) have corresponding incremental reductions in clinical endpoint events
- Sensitivity analyses for endpoints comprised of myocardial infarctions which exclude peri-procedural MIs (Type 4a)
 - Additional analyses factoring for recency and number of prior MIs
- Sensitivity analyses for stroke, factoring for patients with history of stroke
- Sensitivity analyses for heart failure, factoring for patients with history of heart failure
- Sensitivity analyses for endpoints comprised of coronary revascularizations which exclude early elective revascularizations (e.g., within 30-90 days post-randomization)
- Subgroup analyses of primary and potentially key secondary endpoints among the following cohorts:
 - High risk patients with “the hypertriglyceridemic waist” (obese patients at high CV risk)
 - High risk subgroup defined by baseline high-sensitivity troponin T (hsTNT) level (and potentially by N-terminal-pro-brain Natriuretic Peptide [NT-proBNP] from archived frozen samples)
 - High TG/low LDL-C phenotypes beyond those currently specified in the SAP and SAP Addendum

- High-risk patients as defined by their atherothrombotic risk score (Bohula 2016)
- Treatment effect on:
 - Peripheral arterial events (e.g., major adverse limb [MALE] events)
 - Hypertension, using blood pressure (BP) as a continuous variable
- Using archived frozen serum biosamples, additional analyses of fatty-acid levels (and ratios) not currently specified in the SAP Addendum, including baseline and on-treatment effects on EPA, docosahexaenoic acid (DHA), docosapentaenoic acid (DPA), arachidonic acid (AA) (and associated ratios) and relationships between fatty-acid levels and cardiovascular outcomes.
 - Relationship between on-treatment fatty-acid levels and
 - baseline fatty-acid levels and
 - study medication compliance
- Using archived frozen biosamples (serum and whole blood); potential analyses of treatment effects on biomarkers and genetic markers and associations with outcomes, including but not limited to the following:
 - Low density lipoprotein particle number (LDL-P)
 - Remnant lipoprotein cholesterol (RLP-C) (measured)
 - Low density lipoprotein triglyceride (LDL-TG)
 - Oxidized low density lipoprotein (Ox-LDL)
 - Galectin-3
 - Lipoprotein a (Lp(a)) at baseline, as a predictor of CVD benefit
 - Lipoprotein-associated phospholipase-A2 (LpPLA2)
 - High density lipoprotein subfraction 2 (HDL2), high density lipoprotein subfraction 3 (HDL3), apolipoprotein A-I (apo A-I), apolipoprotein A-II (apo A-II), high density lipoprotein particle number (HDL-P), apolipoprotein C-III (apo C-III) (and apo C-III in apo-B containing proteins), apolipoprotein A-V (apo A-V), apolipoprotein E (Apo E) subtypes (2, 3, 4), interleukin 6 (IL-6), lipoprotein lipase (LPL)
 - Analyses may include change (and percent change) from baseline, and on-treatment comparisons between treatment groups with testing as predictors of CV risk
- Exploratory analyses of differential treatment effects for potential benefit (from adverse event reports) of:
 - ophthalmologic changes (e.g., incidence of age-related macular degeneration, progression of diabetic retinopathy)

- cognitive impairment (Schwarz 2018)
- erectile dysfunction (Shim 2016)
- ischemic cardiomyopathy (as indicated by hospitalization for CHF, implantable cardioverter defibrillator [ICD] placement etc.)
- Additional genetic bioassays not included in the REDUCE-IT SAP including genes which may relate to triglyceride, lipid metabolism, and CVD
- Effects of potential mediators identified *post hoc* on primary/key secondary outcome measures (Inzucchi 2018)

